We intend to recruit 52 patients. Participants will be evaluated at 1, 3 and 6 months. At each follow-up visit, patients will have a brief history and physical examination, and any cardiovascular events, including symptomatic AF episodes will be recorded. In addition, the discomfort threshold for tragus stimulation will be obtained to ensure that patients are receiving adequate stimulation. At the 1 month visit, the patients will be interviewed by the unblinded physician or clinical coordinator to address any issues with LLTS administration at home, and to assess their adherence to the stimulation protocol. At the 3 and 6 month visit, patients will have a 5-minute ECG and blood drawn, as during the baseline visit. In addition, patients will undergo noninvasive continuous ECG monitoring for 2 weeks to evaluate their AF burden using an adhesive patch (Zio[®] Patch).

A schematic representation of the study design and timeline of events is shown in Figure 4.

HRV analysis: HRV is a marker of VN activity and can be easily measured by software calculating the distance between consecutive R waves on the ECG ³⁷. Importantly, measures of HRV have been inversely correlated with inflammatory cytokines (C-reactive protein, IL-6) in the general population ³⁸⁻⁴⁰. At each visit, a 5-minute ECG will be obtained for HRV analysis. ECG will be obtained in the supine position after resting for 15 minutes while heart rate, blood pressure and respiration will be monitored. All participants will be asked to avoid caffeine for 4 hours and alcohol, smoking and exercise for 12 hours prior to the visit to avoid any interfering with the results of their ECG. This test will done using a PC-Based ECG device. Analysis and interpretation of the HRV data will be performed in a blinded fashion.

Specific Aim 2: To examine the effect of intermittent (1 hour daily) LLTS on inflammatory cytokines and their gene expression in patients with paroxysmal AF over a 6-month period.

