The same group assignment described in Aim 1 will be used for Aim 2. The importance of this Aim is highlighted by accumulating evidence that inflammation promotes the persistence of AF ^{25,41}. Blood samples (10ml) will be collected at baseline and at 3 and 6 months for cytokine measurement. Samples will be centrifuged (4000g for 10 min), and serum will be stored in aliquots at -20°C until assayed. Patients' serum will be saved frozen and processed in batches of 10 to 12. The investigators performing the cytokine assays will be blinded to group assignment. All assays will be run at the [name] Lab at OUHSC. Inflammatory cytokines, including TNFα, and IL-6, will be measured using commercially available immunoassays analyzed on a flow cytometer (multiplex assays). In addition, peripheral blood mononuclear cells (PBMCs) will be isolated using MACS magnetic bead purification. Inflammatory cytokine gene expression profile will be measured at the above time points, using commercially available microarrays. Finally, we will perform exploratory analyses in order to determine relationships between clinical and cytokine responses to LLTS and identify predictors of response based on baseline cytokine levels. It is known that vagus nerve stimulation attenuates inflammation through the cholinergic antiinflammatory pathway ²⁰⁻²⁴. If this pathway is important in AF as well, we expect that the decrease in cytokines will be correlated with the anti-arrhythmic effect.

Duration of participation

Enrolled patients will participate for a maximum of 7 months with 3 outpatient office visits at 1, 3 and 6 months.

Patient enrollment

[figure not shown]
A maximum of 52 patients meeting the inclusion criteria and not meeting the exclusion criteria will be enrolled in the study. The enrollment period is expected to last for at least 17 months, given that on average 30 patients with paroxysmal AF are seen in our clinics each month and assuming that 1 out of 4 eligible patients would agree to participate in the study.

Data collection and analysis

The final data will be pooled and analyzed by the investigators.

E. Statistical methods

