The primary outcome of this study is the percent of time spent in AF over the monitoring period (AF burden) at the 6-month time point. Secondary outcomes include total duration of AF over the 2-week monitoring period, longest daily duration of AF, measures of HRV and serum cytokine levels. Outcomes will be compared between groups using a Generalized Estimating Equations modeling approach, with 3 time points (baseline, 3 months, 6 months) and 4 terms included in the model (group effect, time effect, group by time interaction, adjustment for baseline measure).

Significant interactions will be followed by time trend analyses stratified by intervention group. If the interaction is not significant, the interaction term will be dropped from the model and the between-group comparisons will be made by combining the 3-month and 6-month data. For all pair-wise testing, we will adjust for multiple comparisons using Tukey's method. The modeling assumptions will be evaluated by plotting the residuals by the predicted values (for the constant variance assumption) and comparing the normal QQ plot with the QQ plot of the residuals (for the normality assumption). If the modeling assumptions are not satisfied, we will perform a natural log transformation of the data, to better satisfy these assumptions. For 0 values, a value of 0.01 will be added to each measure before applying the natural log. Analyses will be based on the intention-to-treat principle. In post-hoc exploratory analyses, we will use logistic regression analysis to identify predictors of clinical and cytokine response to LLTS, defined as a decrease of AF burden and a decrease in cytokines at 6-month follow-up, respectively. Those variables that which are associated with response to LLTS in univariate analysis at p<0.1 will be entered into a multivariate logistic regression model, using a backward elimination method to identify the most parsimonious model. In light of the limited sample size, such analyses will be underpowered and will be considered hypothesis-generating only. Statistical significance will be declared at p<0.05.

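### The search for predictors of response to LLTS models any decrease from baseline with no stated sham contrast, so a cytokine's own baseline can appear predictive through regression to the mean alone

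*Combined protocol and SAP*

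**What the plan says.** Section E (Statistical methods) describes a post-hoc exploratory analysis: "we will use logistic regression analysis to identify predictors of clinical and cytokine response to LLTS". Response is "defined as a decrease of AF burden and a decrease in cytokines at 6-month follow-up", one definition for the clinical response and one for the cytokine response. No minimum decrease is set.

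Selection has two steps. Variables "associated with response to LLTS in univariate analysis at p<0.1 will be entered into a multivariate logistic regression model", and the model is then reduced, "using a backward elimination method to identify the most parsimonious model". Section E also states: "Statistical significance will be declared at p<0.05".

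Section E lists no candidate variables. Section D, under Specific Aim 2, says the exploratory work will "identify predictors of response based on baseline cytokine levels". No other candidate is named.

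Neither section says whether the model uses the active arm or both arms, or mentions a group term, an interaction or a comparison with sham patients for this analysis. Section E adds the caveat that "such analyses will be underpowered and will be considered hypothesis-generating only", and gives limited sample size as the reason.

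**The concern.** A patient whose cytokine level is high at baseline, partly by chance, will tend to have a lower level at 6 months whether or not the stimulation works. If response means any fall from that same baseline, baseline level and response are linked before treatment enters the picture. Only a comparison with sham patients can separate a response to LLTS from ordinary drift back towards the mean, and the plan specifies none here.

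The risk is a report that patients with high baseline cytokines respond to LLTS when nothing of the kind has been shown. Section G says the results may form the basis for a larger trial, where such a finding could influence whom to enrol.

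**Working it through.** **Inputs.** From the documents: 52 patients ("We intend to recruit 52 patients", section D), allocated 1:1, so 26 per arm; response is any decrease; screen at p<0.1; significance at p<0.05. Assumed: the correlation ρ between baseline and 6-month values, which the documents do not give, varied from 0.3 to 0.9.

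**The plan's own figure.** There is none for the responder analysis. The sample size for the primary comparison reproduces. The difference is 28.4 − 3.7 = 24.7 points and the SD is 31.2, so n = 2 × (1.960 + 0.842)² × 31.2² / 24.7² ≈ 25.05, rounded up to 26 per group. Power at 26 is 81.4% by the normal approximation and 79.9% by the noncentral t.

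**Why baseline and decrease are linked.** Let X be the baseline value and Y the 6-month value, with the same normal distribution and no treatment effect.

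- Corr(Y − X, X) = −√((1 − ρ)/2). This is −0.50 at ρ = 0.5 and −0.22 at ρ = 0.9.
- P(decrease | baseline z SDs above the mean) = Φ(z√((1 − ρ)/(1 + ρ))).
- At ρ = 0.5 the multiplier is √(0.5/1.5) = 0.577. A patient 1 SD above the mean is a responder with probability 72%, and one 1 SD below with probability 28%.
- At ρ = 0.9 the multiplier is √(0.1/1.9) = 0.229, giving 59% and 41%.
- Overall, half of untreated patients count as responders.

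**How often the link is declared.** Null trials were simulated (2,000 per setting). Any decrease was regressed on the baseline of the same variable by univariate logistic regression, with n = 26 for the active arm alone and n = 52 for both arms pooled. The table gives the percentage of trials in which baseline appears predictive, for normal data.

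| ρ (assumed) | n=26, LR p<0.1 | n=26, LR p<0.05 | n=26, Wald p<0.05 | n=52, LR p<0.1 | n=52, LR p<0.05 |
|---|---|---|---|---|---|
| 0.3 | 85 | 76 | 64 | 99 | 97 |
| 0.5 | 70 | 58 | 47 | 93 | 87 |
| 0.7 | 52 | 39 | 28 | 76 | 65 |
| 0.8 | 39 | 27 | 18 | 58 | 45 |
| 0.9 | 25 | 18 | 10 | 37 | 25 |

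LR is the likelihood-ratio test. Repeat runs agree to within about 3 percentage points; the widest gap is 37% against 40%, at n = 52 and ρ = 0.9. Lognormal data (log-SD 0.8) give slightly lower LR rates: at n = 26 and p<0.1, 68%, 47% and 22% for ρ = 0.5, 0.7 and 0.9.

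**AF burden, if its baseline were a candidate.** A patient with zero baseline burden can never be a responder. With an assumed shape of 25% zeros and mean about 28, the LR rate at n = 26 and p<0.1 is 86%, 77% and 62% for ρ = 0.5, 0.7 and 0.9. In that setting 39% to 45% of untreated patients count as responders.

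**Does a two-arm interaction cure it?** The continuous 6-month value was regressed on baseline, group and baseline-by-group, with n = 52, no true effect and the interaction tested at p<0.05. False positives are about 4% to 6% for normal and burden shapes. On raw lognormal data they are 11% to 34%. Logged lognormal data are normal, so the rate returns to about 5%.

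**The case against.** Much can be said for the plan. It labels the analysis post-hoc, underpowered and hypothesis-generating. The between-arm question is answered elsewhere in section E by a baseline-adjusted GEE model under intention-to-treat, so an absent LLTS effect would be tested there and could be read beside any predictor result. Passing the p<0.1 screen only admits a variable to the multivariable model; it is not a reported finding.

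These points limit the consequence, and four stronger readings should be set aside.

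- A reader might infer that baseline will appear predictive in most null trials. That depends on a correlation the documents do not give. With 26 patients and the p<0.1 LR test it holds only up to about ρ = 0.7; at p<0.05 with the Wald test it already fails at ρ = 0.5 (47%).
- A reader might infer that sham patients are excluded. The wording suggests an analysis of the active arm, but the plan does not say so.
- A reader might take baseline AF burden to be a planned candidate. It is not named.
- A reader might extend the artefact to baseline cytokines as predictors of AF-burden response. Those are not directly coupled. The defect there is only that a marker of prognosis cannot be told from a marker of response to treatment.

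The core point survives. The caveat in the plan concerns low power, whereas this is a bias, and it grows with sample size: 52% at n = 26 and 76% at n = 52 for ρ = 0.7. Pooling the arms therefore does not help. Nor would a group term alone, because the coupling exists within each arm. The GEE model tests whether LLTS works on average, not who responds.

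**Conclusion.** The concern holds for a cytokine's own baseline as a predictor of a fall in that cytokine. With no treatment effect the p<0.1 screen is passed in roughly 25% to 85% of analyses of 26 patients and 37% to 99% of 52, for assumed correlations from 0.9 down to 0.3, against a nominal 10%. At p<0.05 with 26 patients the LR rates run from 18% to 76%, and Wald rates from 10% to 64%. These are univariate rates for normal data; the full backward-elimination procedure was not simulated. Even at ρ = 0.9 the LR rates are at least 2.5 times nominal.

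The same would apply to baseline AF burden if it were used. For baseline cytokines as predictors of AF-burden response, the conclusion is limited to the missing sham contrast. The primary analysis and its sample size are untouched, so this is a minor but worthwhile correction to an exploratory analysis.

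**What to change.** Replace the responder analysis with a model that uses both arms. Regress the continuous 6-month value on its baseline, group, the candidate and the candidate-by-group interaction. Where the candidate is the outcome's own baseline, the two terms are the same and the baseline-by-group interaction is the one of interest. Put cytokines and other skewed measures on the log scale as a fixed rule, since the raw scale gave 11% to 34% false positives at a nominal 5%.

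List a short set of candidates in advance and report each interaction estimate with its confidence interval. Drop the any-decrease split, the p<0.1 screen and the backward elimination. If a descriptive responder table is kept, show it for both arms side by side.

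The cost is a reworded paragraph in section E and a matching sentence under Specific Aim 2; the data are already to be collected. The downside is that interaction estimates from 52 patients will be imprecise, and the confidence intervals will show it.

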Sample size and power calculations: For purposes of sample size calculations we have simplified the analysis to focus on the AF burden at the 6-month time point between the 2 groups. Assuming a mean±standard deviation AF burden in the control group of $28.4\pm31.2\%$ ³⁴ and a 87% reduction in the LLTS group to 3.7% (assuming a common standard deviation of 31.2%), 26 patients per group would provide 80% power to detect the specified effect sizes at a two-sided significance α level of 0.05. Approximately 30 patients with paroxysmal AF are seen in our clinics each month. Assuming that 1 out of 4 eligible patients would agree to participate in the study, we should be able to enroll the required number of patients within the proposed 17 months, allowing for 6 months of additional follow up and a final month for data analysis.

F. Gender/Minority/Pediatric Inclusion for Research

Participants will be age 21 or older. Race, minority status and gender will not affect enrollment.

[figure not shown]
G. Human participants

The study population will include 52 male/female patients with paroxysmal AF, aged 21 or older, including all races. Since AF is extremely rare in patients less than 21 years old, this age limit is not expected to affect the overall results.

Inclusion Criteria:

- 1. Male and female patients older than 21 year old
- 2. Paroxysmal AF

Exclusion Criteria:

- 1. Left ventricular dysfunction (Left ventricular ejection fraction <40%)
- 2. Significant valvular disorder (i.e., prosthetic valve or hemodynamically relevant valvular diseases)
- 3. Recent (<6 months) stroke or myocardial infarction
- 4. Severe heart failure (NYHA IV)
- 5. Left atrial dilatation (>55mm)
- 6. Recurrent vaso-vagal syncopal episodes
- 7. Unilateral or bilateral vagotomy
- 8. Pregnancy or breast feeding
- 9. Sick sinus syndrome, 2nd or 3rd degree AV block, bifascicular block or prolonged (PR>300ms) 1st degree AV block.
- 2. Identify sources of research material in the form of specimens, records or data.

The research information will consist of the AF burden and serum inflammatory cytokines at each time point specified in the protocol (see Figure 4).

- 3. Describe plans for recruitment and consent procedures to be followed.
- a. Describe the location where consent is most likely to take place (will consent be obtained while an inpatient, in the ER/ICU, will consents be mailed with follow-up meeting to discuss the consent, etc.).

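### The exploratory predictor analyses reduce continuous AF burden and cytokine levels to any decrease, yes or no; a baseline-adjusted 6-month value would use the same data better

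*Combined protocol and SAP*

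**What the plan says.** Section E sets the main outcome on a continuous scale: "The primary outcome of this study is the percent of time spent in AF over the monitoring period (AF burden) at the 6-month time point". Serum cytokine levels are secondary outcomes. Both are compared between groups on their full scale by GEE, with adjustment for baseline.

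For the post-hoc exploratory work the same section changes scale: "we will use logistic regression analysis to identify predictors of clinical and cytokine response to LLTS", with response "defined as a decrease of AF burden and a decrease in cytokines at 6-month follow-up, respectively". It gives no minimum size of decrease and no reason for cutting at zero change. It does not say whether one or both arms enter the model; response to LLTS reads most naturally as the LLTS arm. Candidate variables are screened univariately at p<0.1 and then reduced "using a backward elimination method to identify the most parsimonious model". The plan adds its own caution: "In light of the limited sample size, such analyses will be underpowered and will be considered hypothesis-generating only".

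Specific Aim 2 in section D lists among its exploratory aims to "identify predictors of response based on baseline cytokine levels". The sample size paragraph in section E assumes a control burden of 28.4% (SD 31.2%) and "a 87% reduction in the LLTS group to 3.7" percent, with the same SD in both arms. Entry under Specific Aim 1 needs only two documented AF episodes of 30 seconds or longer within 3 months. No minimum burden on the baseline patch is required.

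**The concern.** A fall of 0.1 percentage points and a fall of 60 points both count as response. A patient with no AF on the baseline patch cannot decrease, so is a non-responder whatever the device does. If LLTS works about as well as the plan assumes, most treated patients will show some fall in burden, and the non-responder class that the logistic model needs becomes small. Univariate screening plus backward elimination on a handful of events is unstable.

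At stake is the exploratory question of who responds. The plan puts the low power down to sample size, but part of it comes from the choice of outcome and can be recovered from data already being collected.

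**Working it through.** **1. The plan's own figure.** The difference is 28.4 - 3.7 = 24.7 points, and 24.7/28.4 = 87.0%. The standardised difference is 24.7/31.2 = 0.792. The normal approximation gives 26 per arm (power 81.4%). The t-test gives n = 26.04, with power 79.9% at 26. The stated 26 per group and 80% reproduce. The 87% is a between-arm difference in 6-month means, not a within-patient fall.

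**2. Expected AF-burden non-responders among 26 LLTS patients, normal model.** Assume that baseline has the control mean and SD, that the common SD is 31.2, and that there is no dropout. The correlation rho between baseline and 6 months is not given, so it is ranged. Then P(decrease) = Phi(24.7 / (31.2 x sqrt(2(1 - rho)))), and expected non-responders = 26 x (1 - P). For rho = 0.5: Phi(0.792) = 0.786, and 26 x 0.214 = 5.6.

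The information kept when a normal outcome is cut so that a share p decreases is phi(z_p)^2 / (p(1 - p)).

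| rho | P(decrease) | non-responders of 26 | P(none) | information lost |
|---|---|---|---|---|
| 0 | 0.712 | 7.5 | under 0.1% | 43% |
| 0.5 | 0.786 | 5.6 | 0.2% | 49.5% |
| 0.7 | 0.847 | 4.0 | 1.3% | 57% |
| 0.8 | 0.895 | 2.7 | 5.5% | 65% |
| 0.9 | 0.962 | 1.0 | 36% | 81% |

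At a 50/50 split the loss is 1 - 0.637 = 36%. It passes one half at about 79% responders. The 36 to 65% range therefore runs from an even split to about 90% responders; rho of 0.9 lies beyond it.

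**3. Bounded burden.** On a 0-100% scale with mean 3.7%, the SD cannot exceed sqrt(3.7 x 96.3) = 18.9 points, so 31.2 is not attainable in the LLTS arm. With beta distributions, an assumed 6-month SD of 4 to 12 points, rho from 0 to 0.9, and values under 30 seconds in 14 days set to zero, the expected number of non-responders is 0.9 to 7.4 of 26.

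Separately, if 10% or 20% of patients had zero baseline burden, that alone would give 2.6 or 5.2 non-responders by construction.

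**4. Power, normal change (cytokine-type case).** The predictor is assumed to correlate r with the change. The documents give no cytokine response rate, so the share decreasing is ranged.

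| setting | continuous | 50% decrease | 70% | 85% | 93% |
|---|---|---|---|---|---|
| n=26, r=0.5 | 76% | 62% | 54% | 41% | 28% |
| n=26, r=0.4 | 53% | 41% | 38% | 29% | 20% |
| n=52, r=0.5 | 97% | 88% | 83% | 69% | 50% |

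**5. Power, bounded AF burden, n=26.** Baseline is beta (28.4, SD 31.2) and 6-month LLTS burden is beta (3.7, assumed SD 5, 8 or 12), linked by a Gaussian copula with rho = 0.5. The predictor is independent of baseline and has latent coefficient 0.45 on the 6-month value.

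- Rank ANCOVA of the 6-month value on baseline and predictor: 72 to 75% with no floor. At SD 12 it falls to 59% if values under 30 seconds are set to zero and to 54% with a 6-minute floor.
- Logistic regression on decrease, yes or no: 14 to 26%.
- Ranks of the 6-month value without baseline: 61 to 64% (no floor).
- Ranks of the change, unadjusted: 8 to 10%.

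The last line matters. Here the predictor acts on a 6-month value with SD 5 to 12, while the change is dominated by baseline with SD 31.2. Keeping the change continuous recovers nothing.

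**The case against.** The strongest reply is that the plan already discounts these analyses. It calls them exploratory, underpowered and hypothesis-generating, and no primary or secondary comparison rests on them. That stands and keeps the point minor. It does not justify a weaker method when a better one needs no new data.

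Four stronger readings are tempting and should not be drawn.

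- **That most of the information is lost.** This holds only beyond about 79% responders. At more even splits the loss is 36 to 50%.
- **That the 87% effect leaves no non-responders.** The 87% compares arm means. An empty class needs rho of about 0.9 or more, or a near-uniform proportional fall in every patient. In the bounded model with rho = 0.5 it occurs in up to about 27% of trials at SD 12 with no floor, but in only about 0 to 11% once values under 30 seconds or 6 minutes are set to zero.
- **That removing the dichotomy alone produces the AF-burden gain.** Step 5 shows otherwise.
- **That the scarcity argument covers cytokines.** The documents give no effect size, SD or response rate for them.

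Nor does the text tie Aim 2's expected correlation between cytokine and antiarrhythmic effects to the binary outcome. The logistic models are described for predictors only.

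**Conclusion.** The point holds as a low-severity improvement. An unexplained cut at zero change replaces two continuous measures, treats trivial and large falls alike, and misclassifies patients who had nothing to lose at baseline. The cost is roughly 36 to 65% of the information under normal theory, and about 1 to 8 AF-burden non-responders among 26. At n=26, power falls from about 76% to 28-62% for a normal change. For AF burden it is 14-26%, against 54-75% with a baseline-adjusted rank analysis of the 6-month value.

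These sizes rest on assumptions that the documents do not supply: rho, the 6-month LLTS SD, the predictor's strength, the share decreasing, the distributional shapes and no dropout. The direction does not depend on any single value in the ranges shown.

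**What to change.** In section E, replace the logistic outcome with the 6-month value: ranks for AF burden, log scale for cytokines. Regress it on the baseline value of the same measure, group, the candidate predictor and the predictor-by-group interaction, using both arms. The interaction makes the result concern response to LLTS rather than prognosis. Where the predictor is the baseline level of the same cytokine, the baseline-by-group interaction is the test. Keep the hypothesis-generating label, and report any responder percentage descriptively by arm without modelling it.

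The cost is a few sentences of statistical wording, with no new data or patients. Results become a slope or rank shift instead of an odds ratio of response. Interaction tests will also have less power than the single-arm figures above, so those figures should not be quoted as the power of the revised analysis.

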The overall objective of this proposal is to translate in ambulatory patients with paroxysmal AF the results of our previous studies showing acute suppression of AF and inflammation in anesthetized canines as well as humans, in order to examine the long-term therapeutic effects of this approach. We hypothesize that intermittent (1 hour daily) LLTS for 6 months may result in long-term decrease of AF burden and suppression inflammatory cytokines in patients with paroxysmal AF. Patients will be randomized to either active or sham LLTS. LLTS will be delivered through a transcutaneous vagus nerve stimulation (tVNS) device for 1 hour daily over a 6-month period. AF burden will be defined as the percent of time spent in AF over a 2-week period, assessed by noninvasive continuous ECG monitoring at baseline, 3 and at 6 months. In addition, blood samples will be collected from patients at baseline, and at 3 and 6 months, for cytokine measurement. These investigations will establish the first evidence of the long-term effects of LLTS on AF suppression in patients with paroxysmal AF and may provide the basis for a potential expansion of the therapeutic targets of this treatment modality beyond AF.

A. Specific aims

[figure not shown]
Specific Aim 1: To examine the effect of intermittent (1 hour daily) LLTS on AF burden in patients with paroxysmal AF over a 6-month period relative to sham LLTS. Patients will be randomized to either active or sham LLTS. LLTS will be delivered through a transcutaneous vagus nerve stimulation (tVNS) device for 1 hour daily over a 6-month period. LLTS will be delivered by the patients themselves at home after individual training. AF burden will be defined as the percent of time spent in AF over a 2-week period, assessed by noninvasive continuous ECG monitoring at baseline, and at 3 and 6 months.

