Patients will be recruited from the inpatient services and outpatient clinics of the University of Oklahoma Health Sciences Center. A meeting with all study personnel to review the study protocol will be held before initiation of the study, as well as every 3-6 months, depending on study progress. Informed consent will be obtained prior to enrollment in the study. The randomization schedule will be implemented with the use of concealed envelopes and it will be stratified by sex. Blocked randomization will be used to decrease the chance of imbalances in the two groups over time.

After informed consent and screening procedures are completed, all patients will undergo noninvasive continuous ECG monitoring for 2 weeks to evaluate their AF burden (the percent of time spent in AF) using an adhesive waterproof continuous monitoring patch (Zio[®] Patch). The Zio[®] Patch (iRhythm Technologies, Inc) is an FDA approved, single-lead, lightweight, 14-day ambulatory ECG adhesive patch monitor. The patch is well tolerated and allows significantly longer continuous monitoring than a regular Holter monitor, leading to an improved AF detection rate ³⁴. After the 2-week monitoring period, patients will be randomly assigned (1:1) to active or sham LLTS. Patients will be blinded to the treatment allocation, and every effort will be made to conceal from the study personnel the nature of the intervention in each study arm. Blinding of the patients will be accomplished by having a sham control arm, in which stimulation will be delivered to a different site (the ear lobe), devoid of vagal innervation ³⁵. By doing so, all patients will be aware that they are receiving stimulation, but they will not be told which site achieves active VN

stimulation. The patients will be requested to refrain from discussing the details of their treatment with other patients in the clinic and with the physicians, nurses and the rest of clinic staff. The clinical coordinator and a clinic physician who will not participate in any of the other study related assessments will be unblinded to the treatment allocation and will instruct the patients on the proper use of the device. These study personnel will be designated to address the patients' questions and concerns as well as to record any side effects related to the use of the device.

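### The 80% power figure pairs an LLTS mean AF burden of 3.7% with an SD of 31.2%, which no 0 to 100% measure can have; the error is conservative at the planned effect, and one sentence needs restating

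*Combined protocol and SAP*

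**What the plan says.** The primary outcome, in Section E (Statistical methods), is "the percent of time spent in AF over the monitoring period (AF burden") at 6 months. The opening overview and Specific Aim 1 give the same scale: "AF burden will be defined as the percent of time spent in AF over a 2-week period".

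The sample size paragraph of Section E says "we have simplified the analysis to focus on the AF burden at the 6-month time point between the 2 groups". Its inputs are a control mean of 28.4% with an SD of 31.2%, and "a 87% reduction in the LLTS group to 3.7% (assuming a common standard deviation of 31.2" percent). Its result is that "26 patients per group would provide 80% power to detect the specified effect sizes" at a two-sided alpha of 0.05. Section D sets the allocation: "After the 2-week monitoring period, patients will be randomly assigned (1:1) to active or sham LLTS".

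The planned analysis is a baseline-adjusted GEE model, with a fallback: "If the modeling assumptions are not satisfied, we will perform a natural log transformation of the data", after adding 0.01 to deal with zeros. Under Patient enrollment, the number is capped: "A maximum of 52 patients meeting the inclusion criteria and not meeting the exclusion criteria will be enrolled in the study". The documents give no separate SD for the LLTS arm and no allowance for loss.

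**The concern.** A percent of time cannot fall below 0 or rise above 100. When the mean of such a measure is close to 0, most patients must be close to 0, and this limits the spread. An SD more than eight times the mean (31.2 / 3.7 = 8.4) is beyond that limit.

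This paragraph is the trial's only justification of sample size. If its two LLTS inputs cannot hold together, the stated power describes no possible trial, and a reader cannot tell what power the plan has at the effect it names. The common SD also hides a consequence of the plan's own means: the two arms must differ in marginal variance, which bears on the constant-variance check in Section E.

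**Working it through.** **Inputs.** From the sample size paragraph of Section E: control mean 28.4, control SD 31.2, LLTS mean 3.7, common SD 31.2, 26 per group, two-sided alpha 0.05. From Section D: 1:1 allocation. From the definition of AF burden: range 0 to 100.

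**1. Reproduce the plan's figure.**
- Reduction: 28.4 x (1 - 0.87) = 3.69, so 3.7 is consistent with 87%.
- Difference: 28.4 - 3.7 = 24.7 points. Standardised: 24.7 / 31.2 = 0.79.
- Two-sample t test, common SD 31.2, 26 per group, 50 degrees of freedom: power 79.9% (normal approximation 81.4%).

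The stated 80% follows from the stated inputs. There is no arithmetic slip.

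**2. Test whether the inputs are possible.** For a variable on 0 to 100 with mean m, the largest SD is sqrt(m(100 - m)). It is reached only when every value is 0 or 100.
- Control: sqrt(28.4 x 71.6) = 45.1. An SD of 31.2 is possible.
- LLTS: sqrt(3.7 x 96.3) = 18.9. An SD of 31.2 is not possible.
- Smallest mean that allows an SD of 31.2: solving m(100 - m) = 31.2² gives m = 10.9. The largest reduction compatible with a common SD of 31.2 is therefore 1 - 10.93 / 28.4 = 61.5%.
- Smallest ratio of marginal variances at the plan's means: 31.2² / (3.7 x 96.3) = 2.7.

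**3. Power with a possible LLTS SD.** The difference stays at 24.7 and the control SD at 31.2. The standard error is sqrt((31.2² + s²) / n), where s is the LLTS SD, and power is from a Welch t test.

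| LLTS SD | 26 per group | 22 per group |
|---|---|---|
| 31.2 (as stated, impossible) | 79.9% | 72.8% |
| 18.9 (ceiling) | 92.1% | 87.0% |
| 10 (assumed) | 96.1% | 92.5% |

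The 22 per group is 26 x 0.85 = 22.1 and rests on an assumed 15% loss; the documents give no rate.

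**4. Check against non-normal data.** At the ceiling the LLTS arm takes only the values 0 and 100, so normal theory is approximate. The simulated LLTS arm had 3.7% of patients at 100 and the rest at 0, with 200,000 replicates. Both control shapes are assumptions and have mean 28.4 and SD 31.2.

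| Control shape | 26 per group | 22 per group |
|---|---|---|
| Beta | 91.1% | 86.4% |
| Two-point (0 or 62.7) | 90.3% | 84.7% |

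Pooled and Welch t tests agree within 0.1 point. At the ceiling, power is thus about 90 to 92% at 26 per group. A smaller LLTS SD raises it, so these figures are lower bounds.

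**The case against.** The strongest reply is that nothing of substance changes. The plan calls its calculation simplified, a common SD is an ordinary planning device, and here it understates power at the stated effect. No patient number, outcome or test is altered. All of this stands, and it keeps the point modest. It does not rescue the sentence: a common SD is a fair simplification only when both arms can have it.

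A second reply is that the ceiling of 18.9% is itself unrealistic. It describes a paroxysmal AF arm in which 3.7% of patients are in AF for the whole two weeks and all others have none. That is also right. The ceiling is a mathematical bound and not a planning value, so power computed there must be worded as a minimum.

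Three stronger readings are tempting, and the documents do not support them.
- **That the trial is underpowered.** Someone who keeps the SD of 31.2% must give up the 87% reduction. At the largest compatible reduction (61.5%, a difference of 17.5 points), power at 26 per group is about 51%. The plan proposes no such effect, so this figure shows where the common SD becomes possible and not what power the trial has.
- **That the analysis must move to the log scale.** The marginal variances differ at least 2.7-fold at the plan's means, which makes unequal residual variance likely. Section E, however, checks residuals of a baseline-adjusted model, so the outcome of that check cannot be settled in advance.
- **That loss to follow-up undermines the sample size.** The cap of 52 equals 2 x 26, so any loss takes the trial below the number powered. With a possible LLTS SD and an assumed 15% loss, raw-scale power at the plan's means still stays above 80%.

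**Conclusion.** The point holds as an impossible planning assumption. An LLTS mean of 3.7% cannot go with an SD of 31.2%; the SD is at most 18.9%. The stated 80% is correct arithmetic on an input that cannot occur, and it is not the power at the plan's own means. At those means, raw-scale two-group power with 26 evaluable patients per group is at least about 90%. The error is conservative at the 87% reduction and gives no ground for saying that 52 patients are too few.

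The bound of 18.9% needs only the definition of AF burden and the stated mean. The power figures also rest on the control mean and SD in the plan, the 87% reduction, and assumed control shapes in the simulation. They do not carry over to smaller effects, to the GEE model, to pooled 3- and 6-month data, or to the analysis of ln(AF burden + 0.01).

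**What to change.** Keep 52 patients and restate the power sentence in Section E, for example:

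> Assuming control AF burden of 28.4% (SD 31.2%) and an LLTS mean of 3.7%, for which the SD cannot exceed 18.9%, 26 evaluable patients per group give at least about 90% power in a two-group comparison of untransformed 6-month AF burden (two-sided alpha 0.05). This is not the power of the GEE model or of an analysis of ln(AF burden + 0.01).

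If the sponsor prefers a smaller, more realistic LLTS SD, state it as an assumption with its reason and the power that results; an SD of 10%, for instance, gives about 96% by normal theory.

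An optional separate sentence could cover loss: with enrolment capped at 52 and an assumed 15% loss (22 per group), at least about 84 to 85% power remains at the same means.

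The cost is rewording one paragraph. Enrolment, outcome and analysis do not change.
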